Protocol Synopsis

Name of Sponsor: Korea Otsuka Pharmaceutical Co., Ltd.	Protocol#
Name of Investigational Medicinal Product: Cilostazol (Pletaal® SR cap.)	021-KOA-1201n
Protocol Title:	A Prospective, Post Marketing Observational Study to evaluate the safety of Pletaal® SR capsule
Clinical Phase:	Post Marketing Observational Study
Treatment Indication:	1. Treatment of ischemic symptoms including ulceration, pain and coldness in chronic arterial occlusion (Berger's disease, arteriosclerosis obliterans, diabetic peripheral angiopathy). 2. Prevention of recurrence of cerebral infarction (excluding cardiogenic cerebral embolism).
Objective(s):	
Pletaal® SR capsule(q.d.) is developed and approved as improving Pletaal® Tablet(b.i.d.). But there is no safety data of Pletaal® SR capsule. The objective of this study is to evaluate following items in relation with use of Pletaal® SR capsule in general medical practice;
 
1. Serious adverse event and adverse drug reaction profile2. Unexpected adverse event/adverse drug reaction profile3. Known adverse drug reaction profile4. Adverse event of product abuse/misuse, drug interactions or overdose5. Other information related to the product safety 
The hypothesis of this study is that Pletaal® SR capsule is safe in the treatment.

Trial Design & Method:	This is a Post Marketing Observational Study of cilostazol (Pletaal® SR capsule). This study will be conducted in a prospective, single-arm, multi-center format. As this study is observational in nature to collect the safety data after administrating the Pletaal SR capsule, from baseline to 16 weeks. The patient's follow-up is not prescriptive in nature and must be left up to the judgment of the physician (investigator), within the period of observation set forth in the protocol.
Trial Population:	At least 3000 patients will be enrolled for this study to collect the safety data among various groups. Investigators across the country will be participating in this study and the number of patients to be enrolled by each investigator will vary.

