
Inclusion/Exclusion Criteria:
	
Inclusion Criteria
 
Patients must meet all of the following inclusion criteria to be eligible for enrollment into the study :
 
 1. Patients who are prescribed Pletaal® SR capsule treatment as per investigator's medical judgment for adults aged 19 and over. 2. Patients who gave written authorization to use their personal and health data 
Physician (Investigator) will refer to the product market authorization (package insert) for inclusion criteria.
 
Exclusion Criteria
 
Patients presenting with any of the following will not be included in the study
 
 1. Patients with hemorrhage 2. Patients with congestive heart failure 3. Patients with known hypersensitivity to Cilostazole or any ingredients of Pletaal® 4. Women who are pregnant or may possibly become pregnant 5. Patients who is not eligible to participate this study as investigator's medical judgment 
Physician (Investigator) will refer to the product market authorization (package insert) for exclusion criteria.

Investigational Medicinal Product(s), Dose, Dosage regimen, Treatment period, Formulation, Mode of Administration:
	
The usual adult dose of Pletaal® SR capsule is 200mg of cilostazol, once daily, by the oral route. This is taken in the fasting state, avoid eating.

Safety Measure:	
1. The incidence rate and the number of AE/ADRs2. The incidence rate of Tarchycardia and Palpitation after Pletaal® SR capsule administration3. The number and percentage of drop-out patients according to AEs4. The difference between AE and drug compliance according to patient's character
-----------------	---

Statistical Methods:	1. Demographic Information & Baseline Characteristics
	Data for the baseline characteristics is demonstrated by descriptive statistics. Mean, standard deviation(SD), minimum value, median, maximum value for continuous variables and frequency(n), percentage(%) for categorical variables will be presented in overall patients.
	2. Safety Analysis
	
 - The incidence rate and the number of AE/ADRs - The incidence rate of Tachycardia and Palpitation after Pletaal® SR capsule administration - The number and percentage of drop-out patients according to AEs - The difference between AE and drug compliance according to patient's character

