	
All adverse events (AEs) observed during/after the administration will be analyzed as safety assessment. The number of patients and the number of AE/ADR, SAE/Serious ADR (SADR), unexpected AE/ADR will be calculated (frequency and percentage). In the final report, the incidence rate of all AEs during the study period will be estimated with its 95% confidence interval.

	
The number and percentage of drop-out patients according to AEs and the incidence rate of AEs for the severity will be estimated. Safety measures will be summarized and analyzed to find the risk factors in overall patients by background factors (baseline characteristic, drug administration, concomitant drug treatment etc.). The analysis will be performed using Chi-square test or Fisher's exact test.

	
The number and percentage of AEs/ADRs will be summarized for special population (elderly patients, patients with liver or renal disease).

	
Record the term of adverse event according to the System Organ Class, Preferred Term, Lower-Level Terms in the Medical Dictionary for Regulatory Activities (MedDRA). If there is no preferred term, look up the WHO Adverse Reactions Terminology (WHOART).

Estimated Duration of study	
Planned study schedule is as below;
 
1. Study duration: Jan 2013 – Dec 20142. Submit the final reports to KFDA: within 1 year of study completion3. Submit the CSR to global within one year after LPLV or end of data collection as defined in protocol or contract
-----------------------------	--

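### The risk-factor analysis names only significance tests: no contrast with a confidence interval is planned for any background factor or special population

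*Protocol*

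**What the plan says.** All of this is in the Protocol Synopsis, mostly under Statistical Methods, 2. Safety Analysis.

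- The aim is inferential: "Safety measures will be summarized and analyzed to find the risk factors in overall patients by background factors". Baseline characteristics, drug administration and concomitant treatment are given as examples of such factors.
- The next sentence fixes the method: "The analysis will be performed using Chi-square test or Fisher's exact test". No measure of association, interval or model is named with it.
- The only interval in the document belongs to a single overall quantity: "the incidence rate of all AEs during the study period will be estimated with its 95% confidence interval".
- A separate sentence deals with the special populations: "The number and percentage of AEs/ADRs will be summarized for special population (elderly patients, patients with liver or renal disease"). It names no test, comparison group or interval.
- The list of safety measures includes "The difference between AE and drug compliance according to patient's character", but does not say on what scale that difference is measured.
- On size, the Trial Population row says "At least 3000 patients will be enrolled for this study to collect the safety data among various groups". No significance level, power, AE rate, effect size or factor prevalence accompanies the number.

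**The concern.** The stated aim and the stated method do not fit well. Finding risk factors for a safety report means saying how much more often AEs occur with a factor than without it, and how precisely that is known. Neither named test estimates this. A chi-square or Fisher p-value combines the size of the excess with the number of patients who carry the factor, so the same relative risk can be significant for a common factor and not for a rare one.

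Two misreadings are at stake. A non-significant result in a small group may be taken as reassurance when the data still allow a large excess. A modest excess tied to a common factor may stand out only because the factor is common. For the elderly, liver and renal groups, a percentage on its own shows neither a comparison nor its uncertainty. The synopsis says that safety data on this formulation are lacking and takes as its hypothesis that the product is safe, so careless reading of null tests is a practical hazard.

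**Working it through.** **No figure to reproduce.** The target of at least 3000 comes without a derivation, so the check is of the mechanism: how far does significance depend on how common the factor is?

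**Inputs.** From the protocol: total N = 3000, single arm. Assumed, because the protocol gives none of them: two-sided level 0.05, AE risk without the factor (10% in step 1, 1% to 20% in step 2), and the number of patients carrying the factor.

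**Formulas.** With a events in n1 carriers and b events in n2 non-carriers, write p1 = a/n1, p0 = b/n2, and P = (a + b)/(n1 + n2).
- Uncorrected chi-square as a z statistic: z = (p1 − p0) / √[P(1 − P)(1/n1 + 1/n2)].
- Risk ratio RR = p1/p0, with 95% CI RR × exp(±1.96 × SE), where SE = √(1/a − 1/n1 + 1/b − 1/n2).
- Risk difference p1 − p0, with 95% CI ± 1.96 × √[p1(1 − p1)/n1 + p0(1 − p0)/n2].

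**Step 1: observed results, 10% risk without the factor.**

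*Factor in 1500 patients, 184/1500 against 150/1500.* RR = 0.1227/0.1000 = 1.23. P = 334/3000 = 0.1113 and z = 0.02267/0.01149 = 1.97, so p = 0.048. SE = 0.1038, giving a 95% CI for RR of 1.00 to 1.50. This is the smallest count that is significant by chi-square; Fisher's test gives 0.055, so the choice between the two tests matters at the boundary. At 12.5% against 10% (188/1500 against 150/1500), RR is 1.25 (1.02 to 1.53) and the chi-square p is 0.028.

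*Factor in 90 patients (3%), 14/90 against 291/2910.* RR = 0.1556/0.1000 = 1.56. P = 305/3000 = 0.1017 and z = 0.05556/0.03234 = 1.72, so p = 0.086 (Fisher 0.107). SE = √(0.0714 − 0.0111 + 0.0034 − 0.0003) = 0.252, giving a 95% CI for RR of 0.95 to 2.55. The risk difference is 5.6 percentage points (−2.0 to 13.1).

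*Factor in 30 patients (1%), 6/30 against 297/2970.* RR = 2.00 (0.97 to 4.12), chi-square p = 0.071, Fisher p = 0.115.

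The larger observed ratios are the non-significant ones. The interval shows what the p-value hides: in the second case, an excess of up to about two and a half times remains compatible with the data.

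**Step 2: power for a true doubling of risk, over a range of AE risks.** Power = Φ[(|p1 − p0| − 1.96 × se0)/se1], with se0 the pooled standard error above and se1 the unpooled one.

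Worked case, 30 carriers, 1% against 2%: P = (0.6 + 29.7)/3000 = 0.0101, se0 = 0.01835, se1 = 0.02563. The argument is (0.01 − 0.03596)/0.02563 = −1.01, so power is 16%.

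| AE risk without / with factor | 30 carriers | 150 carriers | 1500 carriers |
|---|---|---|---|
| 1% / 2% | 16% | 28% | 62% |
| 5% / 10% | 30% | 71% | over 99% |
| 10% / 20% | 46% | 93% | over 99% |
| 20% / 40% | 73% | over 99% | over 99% |

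The normal approximation is rough where few events are expected. For 10% against 20%, exact Fisher power is 39% with 30 carriers and 93% with 150. In every row the same relative risk is much easier to detect in the common factor, so the direction does not rest on the 10% figure; the size does depend on the AE risk.

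**The case against.** The strongest reply is that the document is a synopsis and that naming two tests does not exclude a risk ratio and interval beside them; a statistical analysis plan could add both. The safety measures are also to be summarized by background factor, so incidences with and without each factor will probably be visible. A reader who sees 15.6% against 10.0% can form the ratio unaided. Low power in small groups comes from their size and no reporting change will cure it. These points stand, and they limit the weight of the finding. They do not remove it. The protocol is not merely silent here: it states an aim and a method that suits the aim poorly, and it plans an interval for overall incidence but none for its comparisons. Two percentages do not show the uncertainty of their contrast.

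A reader might infer more than the text supports. One might say that the plan decides risk factors at p < 0.05 and clears the rest. The protocol gives no significance level, no rule for declaring a factor and no rule for ruling one out. One might also say that liver disease would be dismissed by a test in too few patients. The sentence naming liver disease asks for a number and percentage, not a test. Liver disease would be tested only if it were also taken as a background factor, which the open-ended list of factors permits but does not state.

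**Conclusion.** The point holds as a mismatch between aim and method. For background factors, the only analysis named beyond summaries is a test of association, with no effect measure or interval. For elderly, liver and renal patients there is description only, with no contrast against patients outside the group.

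In the illustration, a ratio of 1.23 in a factor held by half the patients is significant by chi-square, while 1.56 in 90 patients is not and leaves 2.55 within its interval. Power for a doubled risk in 30 patients runs from about 16% to 73% as the assumed AE risk goes from 1% to 20%. These sizes rest on assumed AE risks, prevalences and a 0.05 level that the protocol does not give; only N = 3000 is its own. The data collected and the patients enrolled are unaffected. What is at stake is how the results by factor are reported and read, so this is a cheap improvement rather than a flaw that undermines the study.

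**What to change.** Amend the risk-factor and special-population text in Statistical Methods, 2. Safety Analysis, along these lines:

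*For each background factor, and for elderly patients and patients with liver or renal disease compared with patients outside the respective group, the report gives the group sizes, the patient-level incidence with and without the factor, and the risk difference and risk ratio with 95% confidence intervals. Chi-square or Fisher p-values are supportive. A non-significant result in a small group is not reported as absence of risk; the upper confidence limit states the excess still compatible with the data.*

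The same 2x2 tables supply all of this, so no further data or patients are needed. The downside is that wide intervals for small groups become visible and conclusions about them will be less reassuring. The change does not raise power in those groups; it shows how little can be concluded there.
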